4. STUDY DESIGN

Provide a detailed description of the study design (e.g. cross-sectional, stratified, longitudinal, prospective cohort, case-control, randomized, placebo-controlled, masked/double masked, feasibility, pilot, proof-of-concept, etc.).

Explain why this study design is appropriate for this study.

Response: We will employ a double-blind, placebo-controlled, randomized, cross-over study to objectively determine the clinical response to sodium oxybate in ETOH+ SD and SD/VT patients compared to patients with ETOH- SD and SD/VT.

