5. SUBJECT INFORMATION

a) Target Enrollment- Specify the number of subjects you plan to enroll and justify why this number is sufficient to achieve adequate power for statistical analysis taking into account anticipated screen failures and drop-outs. Include sample size by cohort if the study has multiple cohorts.

Response: Specific Aim #1: To estimate the number of patients in this study, we reviewed our open-label study, in which sodium oxybate improved voice symptoms in 82.2% (37 out of 45) of ETOH+SD and SD/VT patients (p = 0.001). To our knowledge, no other studies have examined the benefits of sodium oxybate in SD and SD/VT. Using an estimated effect size based on values from this study, a binomial test found that a power of 80% at a significance level of 0.0125 will be obtained with 22 patients for the proposed study. To account for a potential patient dropout based on our prior study, we will recruit up to 35 patients per cohort. The total of recruited patients will be up to 140 (4 cohorts x 35 patients/cohort).

b) If this is a multi-center study and other sites rely on the MEE HSC as the IRB of record, please specify the total number of subjects required by all sites to achieve sufficient power.

Response: N/A

c) Provide justification that the researchers have access to sufficient numbers of eligible subjects to meet target enrollment goals (e.g., researcher's own patients, clinic patients with a specific diagnosis, subjects from previous studies who agree to participate in future studies).

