9. STUDY PROCEDURES

a) Provide a detailed description of all study procedures and intervention(s) each subject and/or cohort will experience. Provide a schedule of visits and the procedures that occur at each visit (e.g., tests, questionnaires, surveys, imaging or other interventions.). If the study also involves standard of care, differentiate between research only procedures and standard of care.

Response:

Determine the clinical response of SD and SD/VT symptoms to sodium oxybate using a double-blind, placebo-controlled, randomized, cross-over study design.

The experimental design includes (1) screening for study eligibility; (2) an objective standardized alcohol challenge test for assessment of symptom responsiveness to alcohol, and (3) a double-blind, placebo-controlled, randomized, crossover study of sodium oxybate. The **primary outcome** will be to determine the response of SD and VT symptoms to sodium oxybate 40 min after administration, compared to placebo. We will recruit the following groups of patients:

- (1) ETOH+ SD and SD/VT who report positive effects of alcohol on their voice symptoms;
- (2) ETOH- SD and SD/VT who report no effects of alcohol on their voice symptoms, and Although our prior studies have shown that sodium oxybate has similar effects in both SD and SD/VT patients as well as in ADSD and ABSD, the inclusion of these patients will allow to capture the entire SD populations and to cross-validate our findings. On the other hand, the inclusion of negative controls with ETOH- SD and ETOH- SD/VT will allow for enhanced explanations of our findings and delineation of the primary factors contributing to the pathophysiology of SD and VT with respect to treatment outcome.

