11. HYPOTHESES

Hypotheses are more specific than specific aims and are tested using predetermined statistical methods and form the basis for statistical power calculations. The primary hypothesis is a statement of the effect of the research intervention/interaction on the primary outcome measure. Hypotheses are generally stated as the null and alternative hypotheses (H0, Ha) as they have their basis in inferential statistics. Rejecting the null hypothesis with a specific level of probability indicates that there is a relationship between the variables being studied. State the alternative hypothesis which you expect your data to support.

Examples of null and alternative hypotheses

- H0: Chronic sinusitis prevalence rates are not different among children from low and high socioeconomic groups
- Ha: Chronic sinusitis prevalence rates are different among children from low and high socioeconomic groups.
- a) Describe the primary hypothesis:

Response: H0: Similar to alcohol and placebo, sodium oxybate is not effective in reducing LD symptoms in EtOH+ patients but not EtOH- patients.

Ha: Similar to alcohol and in contrast to placebo, sodium oxybate is effective in reducing LD symptoms in EtOH+ patients but not EtOH- patients.

b) Describe any secondary hypotheses.

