12. STATISTICAL METHODS

Describe the planned statistical methods including specific tests (e.g., parametric and non-parametric tests, estimation of incidence and prevalence rates, odds ratios, survival/failure analyses, intent to treat analyses). Provide the power calculations used to estimate the proposed sample size. If needed, please consult a biostatistician. (Note: Biostatistical consults are available through Harvard Catalyst.)

Response:

Audio recordings will be de-identified, randomized and blindly rated to count the voice breaks as well as to quantify harshness, breathiness, tremor, and hoarseness using a visual analog scale with three gradation indicators along a 100-mm line (normal, modulates voice, offsets voice), with distance in mm denoting the degree of deviancy from normal, as described earlier (Kirke et al., 2016). Alcohol Challenge Test. All individual measures before and after alcohol intake will be compared using the equation ((Baseline-Alcohol Challenge)/Baseline) \times 100%. To account for potential subjective bias and ensure reliable alcohol effects on voice symptoms, we will consider patients with \geq 10% change of their symptoms from baseline as responsive to alcohol (ETOH+) (Haubenberger et al., 2013; Voller et al., 2014). As a secondary outcome, we will compute Pearson's correlations between symptom scores and brAC measures to examine the baseline and each time point in respect to alcohol content at a corrected p \leq 0.05.

Analysis. The primary outcome within each group will be examined using a linear mixed effect model with treatment (sodium oxybate and placebo) and treatment visits as interacting fixed effects and a per subject random effect at overall $p \le 0.01$ to correct for multiple comparisons. If the interaction between the fixed effects is significant, the difference between treatments will be tested using linear contrasts of least-squares means for the fitted model at $p \le 0.05$ adjusted for multiple comparisons. As a secondary analysis, benefit ratio will be calculated as (sodium oxybate effect – placebo effect) and analyzed using a Friedman test at $p \le 0.01$.

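### The primary hypothesis says oxybate helps ETOH+ but not ETOH- patients, yet every planned test is drug versus placebo within a group, so the second half has no valid test

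*Combined protocol and SAP*

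**What the plan says.** Section 11 states one hypothesis. Its alternative is that, like alcohol and unlike placebo, "sodium oxybate is effective in reducing LD symptoms in EtOH+ patients but not EtOH- patients". Section 4 gives the purpose of the design as to "objectively determine the clinical response to sodium oxybate in ETOH+ SD and SD/VT patients compared to patients with ETOH- SD and SD/VT". Section 9 explains why ETOH- patients are enrolled: "the inclusion of negative controls with ETOH- SD and ETOH- SD/VT will allow for enhanced explanations of our findings". Section 5 plans "up to 140 (4 cohorts x 35 patients/cohort"), so if the four cohorts are ETOH status by diagnosis, up to half of the patients are there for this contrast.

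Section 12 gives the analysis: "The primary outcome within each group will be examined using a linear mixed effect model". The fixed part of that model holds treatment, visit and the interaction of the two; subject enters as a random effect, and the overall level is 0.01. If that interaction is significant, "the difference between treatments will be tested using linear contrasts of least-squares means" at an adjusted 0.05. The secondary analysis is a Friedman test on the oxybate effect minus the placebo effect. ETOH status is not a model term anywhere, no contrast between ETOH groups is named, and no margin is given for concluding that the drug does not work in ETOH- patients.

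**The concern.** The hypothesis is about two groups, but each planned test looks inside one group at a time. Under this plan the ETOH- part can be supported only by failing to reject in ETOH-. Two errors follow. A significant result in one group and a non-significant one in the other does not show that the effects differ. A non-significant result in ETOH- does not show that the effect there is zero or negligible.

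At stake is the claim that alcohol response identifies who benefits. Readers could take the within-group results as evidence of selectivity when the drug helps both groups equally, or helps ETOH- patients somewhat less. How likely that is depends on what Section 12 means by each group: the two ETOH groups listed in Section 9, or the four cohorts counted in Section 5. The plan does not say.

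**Working it through.** **The plan's own figure.** Section 5 gives 22 patients for 80% power at 0.0125 by a binomial test, from 37/45 = 82.2% responders. The null proportion and sidedness are not stated. With an assumed null of 0.5 and a one-sided exact test, 22 reproduces: reject at 17 or more of 22, actual alpha 0.0085, power 81.6%. (Two-sided, power at 22 is 64.9% and 26 are needed.) The calculation concerns the ETOH+ response rate alone. It contains no ETOH- rate and no comparison.

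If that same rule were applied to both groups with 82.2% response in each, the chance of success in ETOH+ and failure in ETOH- would be 0.816 × (1 − 0.816) = 15%.

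**Assumptions for the continuous outcome.** Effects are mean paired differences in units of their SD. A value of 0.78 is roughly what 22 patients detect with 80% power at 0.0125; 0.5 and 0.6 are more modest. Sample sizes per group are 22 (the Section 5 calculation), 35 (one full cohort), 44 (two cohorts of 22 pooled) and 70 (two full cohorts pooled).

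**Formulas.**
- Within-group power: non-central t with df = n − 2 and non-centrality d√n, two-sided 0.01.
- False pattern under equal effects: power × (1 − power).
- Interaction: difference of two mean paired differences, SE = √(1/n₁ + 1/n₂), df = n₁ + n₂ − 4.

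Example, n = 22 and d = 0.6: non-centrality 0.6 × √22 = 2.81, critical t 2.845, power 0.502, false pattern 0.502 × 0.498 = 25%.

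**Results at 0.01.** The first three rows assume the same true effect in both groups.

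| | 22 per group | 35 | 44 | 70 |
|---|---|---|---|---|
| False pattern, 0.5 SD | 22% | 24% | 20% | 6% |
| False pattern, 0.6 SD | 25% | 17% | 10% | 1% |
| False pattern, 0.78 SD | 17% | 3.5% | 0.8% | <0.1% |
| Real ETOH- effect of 0.4 SD missed | 80% | 63% | 51% | 25% |
| Hypothesised pattern when ETOH+ is 0.78 and ETOH- is half of it | 64% | 63% | 53% | 27% |
| 95% interval half-width, SD | 0.44 | 0.34 | 0.30 | 0.24 |

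An interaction test would falsely favour ETOH+ 0.5% of the time at two-sided 0.01 (2.5% at 0.05), whatever the group size. A simulated two-period crossover with balanced sequences agreed with the false-pattern rows to within about half a percentage point.

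In the half-effect row the groups do differ, but the statement that the drug does not work in ETOH- patients is false, and the plan would usually appear to support it at 22, 35 or 44 per group.

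**The case against.** There is a fair case that this is less serious than it looks. The only specific aim (Section 2) is the clinical response to oxybate, and Section 9 defines the primary outcome against placebo. That comparison in ETOH+ patients is not affected. This stands, and it limits the damage to the second half of the hypothesis. It does not remove the problem, because Section 11 states no other hypothesis and Section 4 promises the comparison.

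Second, the record of amendment AME11 speaks of two experimental groups, which together with Section 9 favours pooling SD and SD/VT. Pooled, at 0.78 SD, the false pattern is only 0.8% (44 per group) or below 0.1% (70). That also stands. Against it, Section 5 counts four cohorts and its 0.0125 equals 0.05/4. At 0.5 SD the pooled risk is still 20% or 6%. Pooling does nothing for the lack of a margin.

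Third, the figures model a simple paired test at 0.01, not the two-step route in Section 12. At an unadjusted 0.05 the false pattern for 0.5/0.6/0.78 SD is 24%/18%/6% at 22 per group, 15%/6%/0.6% at 35, 9%/3%/0.1% at 44 and 1.5%/0.1%/<0.1% at 70. These are mostly lower, and the unstated adjustment and the gating step would move them again. All of these numbers should be read as illustration; the logical gap does not depend on them.

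Fourth, the Friedman analysis might seem to supply the comparison. It does not: it is a within-subject method for repeated measures, and no group factor is named.

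**Conclusion.** The concern holds. Half of the only stated primary hypothesis has no valid test and would rest on a difference in significance between two separate analyses. Under equal true effects, the misleading pattern occurs in roughly 15% to 25% of trials at 22 per group, for the effects and rules considered at about the planned alpha. With diagnoses pooled, full enrolment and a large effect it becomes negligible. These sizes rest on assumed standardized effects, two-sided testing and a simple paired analysis. The failure to distinguish a non-significant result from no effect rests on none of these assumptions. The drug-versus-placebo conclusion in ETOH+ patients stands as planned. This must be corrected before unblinding.

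**What to change.** Keep the ETOH+ drug-versus-placebo test. In Sections 11 and 12:

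1. Add one model over all patients, SD and SD/VT pooled with diagnosis as a factor, containing treatment, period (visit), sequence, ETOH group and treatment-by-ETOH group. Name that interaction as the test of selectivity.
2. Place it in the multiplicity rule, for example at 0.01 and only after the ETOH+ test succeeds, so that no alpha is split.
3. Report the ETOH- effect with its confidence interval. Claim ineffectiveness only if the interval excludes a worthwhile effect stated in advance.
4. Define each group, and reword H0 as the complement of Ha, which it currently is not.

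If the sponsor does not want this test, the alternative is to narrow Ha to ETOH+ patients and present the ETOH- results descriptively.

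**Cost.** Wording only, on the same data, and the ETOH+ test loses nothing. The price is modest power. For a true difference of 0.78 SD, interaction power at 0.01 is 46%/73%/84%/98% with 22/35/44/70 per group (71%/90%/95%/99.6% at 0.05). Requiring ETOH+ success first gives 44%/72%/84%/98% at 0.01. If ETOH- patients have half the ETOH+ effect, power at 0.01 falls to 9%/16%/22%/38%. With no true ETOH- effect and an illustrative margin of 0.39 SD, the 95% interval excludes the margin in about 41%/61%/71%/90% of trials. The selectivity claim is therefore workable only with the diagnoses pooled, and at 22 per group it would fail more often than succeed. ETOH status is observed, not randomized, so a significant interaction would show that the effect varies with that trait, not that the trait causes the difference.

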Enrollment and Eligibility Screening. Patient eligibility will be established based on the initial screening interview and the review of medical information, including laryngological and neurological examinations. Any subject with neurological (other than SD or dystonic VT in the patient groups), laryngeal, or a history of psychiatric problems will be excluded from the study. All patients will be right-handed, native English speakers according to the standardized Edinburgh Handedness Inventory (Oldfield, 1971), which will be important in examining drug-induced central effects during speech production. Because brain and laryngeal surgery may influence functional brain organization, all patients with a history of brain and/or laryngeal surgery will be excluded from the study. To avoid the possibility of confounding effects of drugs that act upon the central nervous system, patients who receive any medication(s) affecting the central nervous system will be excluded from the study. All patients will be asked to abstain from consuming any alcohol or caffeine (or foods with caffeine such as chocolate) for at least 48 hours before the study visits.

General Study Procedures. Eligible patients will require three visits, including one for the alcohol challenge test and two for sodium oxybate and placebo treatments (**Fig. 1**). At their initial baseline, all patients will be assessed for vital signs (blood pressure, pulse, height and weight); cognitive and

[figure not shown]

Fig. 1. Flowchart of study procedures. ETOH+ alcohol-responsive; ETOH- alcohol-non-responsive.

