Randomization and Allocation. Following the alcohol challenge, patients will be randomized for the double-blind, placebo-controlled, cross-over study. The randomization will be performed by the MEEI Research Pharmacy and will be blinded for the investigators and patients. The study will be conducted under the existing Investigational New Drug (IND) application granted to the PI by the US Food and Drug Administration (FDA) for the use of sodium oxybate in SD and SD/VT patients (#117,954). Patients will be allocated 1:1 to a treatment sequence #1 of sodium oxybate/placebo or sequence #2 of placebo/sodium oxybate. Jazz Pharmaceuticals, Inc., will provide sodium oxybate and the matching placebo for research purposes, which will be sent directly to the MEEI Research Pharmacy. The placebo will be a clear solution with salty taste that matches the appearance and taste of the drug. Sodium oxybate (1.5 g = 3 ml) of oral solution diluted in 47 ml of water) and the placebo (50 ml) will be formulated in sequentially numbered containers by the research pharmacy in the morning of administration. Both patients and investigators will be blinded until all outcome data are processed and the database is locked at the end of the study. EPIC will be used for study drug dispensing to ensure accurate and complete documentation.

Study drug will be administered by a licensed physician associated with this protocol.

As stated above under the *General Study Procedures* section, all patients will be assessed for their vital signs, MoCA, C-SSRS, side effects, and sleepiness immediately before and 45, 180, 300 min after drug/placebo intake. As a primary outcome measure, voice and speech recordings will be performed at the same time points. Data will be de-identified, randomized, and blindly rated for symptom severity, as described above. Our prior studies have shown that the effects of sodium oxybate (1-1.5 g) in ETOH+ movement disorders are obvious 30-45 min following drug intake and last approximately 3.5-4 hours (Frucht et al., 2005a; Frucht et al., 2005b; Arpesella et al., 2009; Simonyan and Frucht, 2013; Rumbach et al., 2016).

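### The primary mixed model has no visit-level error term, so if several recordings per visit enter it, the averaged treatment test is too liberal and the treatment-by-time interaction test is too conservative.

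*Combined protocol and SAP*

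**What the plan says.** Section 12 (Statistical Methods) analyses the primary outcome within each group with a linear mixed model that has "treatment (sodium oxybate and placebo) and treatment visits as interacting fixed effects and a per subject random effect". The overall level is 0.01, set "to correct for multiple comparisons". Beyond "a per subject random effect", it names no visit-within-subject effect and no within-visit covariance. On the order of testing it says: "If the interaction between the fixed effects is significant, the difference between treatments will be tested using linear contrasts of least-squares means". Those contrasts use an adjusted 0.05.

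Section 9 (Study Procedures) gives the data structure. On visits: "Eligible patients will require three visits, including one for the alcohol challenge test and two for sodium oxybate and placebo treatments". Assessments fall "immediately before and 45, 180, 300 min after drug/placebo intake", and "As a primary outcome measure, voice and speech recordings will be performed at the same time points". Each patient therefore has one visit per treatment and four recordings at each. Earlier in section 9 the primary outcome is the response 40 minutes after administration, compared with placebo. That is a single time point, and the recording schedule lists 45 minutes rather than 40. Section 10 describes the outcome only as clinical improvement of voice symptoms.

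The documents do not say whether all four recordings, the three post-dose ones, changes from pre-dose or only the 40/45-minute value enter the model. They do not say whether the treatment-visit factor is the period or the time point. They give no variance components.

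**The concern.** Treatment changes only between visits. The recordings of one visit share one administration and one day's voice state. A subject intercept captures what a patient's two days have in common, but not what separates them. If several recordings per visit enter the model, it treats them as nearly independent replicates of the treatment comparison.

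Two errors follow, in opposite directions. The standard error of a treatment effect averaged over recordings is too small, so its interval is too narrow and its 1% level is not kept. The day variation that spills into the residual makes the error term of the treatment-by-time interaction too large. That interaction, if the treatment-visit factor means time point, is what section 12 tests first.

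**Working it through.** **The plan's own figure.** Section 5 gives 22 patients from a binomial test with 37/45 = 82.2% response, 80% power and level 0.0125. An exact one-sided test against an assumed null rate of 0.5 rejects at 17 or more of 22 (exact level 0.0085) and has power 81.6%, so 22 reproduces. It does not come from the mixed model and says nothing for or against this point. It supplies only n = 22, with n = 35 as the recruitment ceiling per cohort.

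**Inputs.** Two treatment visits per patient; m = 4 recordings per visit, or m = 3 post-dose (section 9); nominal level 0.01, taken as two-sided (section 12 does not say). The share ρ of within-subject variance common to one visit is not in the documents. I assume 0.1 to 0.5 and write v = ρ/(1−ρ), the ratio of day variance to recording variance.

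**Treatment effect averaged over recordings.** In a balanced design with the subject effect removed, the residual mean square is inflated by k = 1 + mv/(2m−1). The true variance of the treatment effect is proportional to 1 + mv. So

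true variance / model variance = (1 + mv)/k, and the true rejection rate ≈ 2·[1 − Φ(2.576/√ratio)].

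Example with m = 4, ρ = 0.5: v = 1, k = 1 + 4/7 = 1.571, ratio = 5/1.571 = 3.18, √3.18 = 1.784, 2.576/1.784 = 1.444, rejection rate 14.9%.

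| ρ (assumed) | m = 4: ratio | m = 4: rejects at 1% | m = 3: rejects at 1% |
|---|---|---|---|
| 0.1 | 1.36 | 2.7% | 2.1% |
| 0.15 | 1.55 | 3.9% | 2.9% |
| 0.2 | 1.75 | 5.2% | 3.7% |
| 0.3 | 2.18 | 8.1% | 5.6% |
| 0.5 | 3.18 | 14.9% | 10.3% |

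With m = 4 the model's standard error is 0.86 (ρ = 0.1) down to 0.56 (ρ = 0.5) of the true one. Simulation under the null at m = 4, ρ = 0.5 gives 14.6% (n = 22) and 14.9% (n = 35), so sample size hardly matters.

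**Three changes from a shared pre-dose value.** The day effect cancels, but the pre-dose recording's own error is common to all three changes, with the same variance as each post-dose error. That is v = 1 with m = 3 for any ρ: ratio = 4/1.6 = 2.5, rejection 10.3%. Simulation gives 10.6% (n = 22) and 10.1% (n = 35).

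**Drug-placebo contrast at 45 minutes inside the four-time model.** Variance ratio = (1 + v)/k. At ρ = 0.1 it is 1.111/1.063 = 1.04; at ρ = 0.5 it is 2/1.571 = 1.27. Rejection is 1.2% to 2.2% at the 1% level and 5.5% to 8.2% at the 5% level.

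**Interaction.** Day variance cancels from the true variance of treatment by time, but the model still divides by a residual inflated by k (1.06 to 1.57 for m = 4). Simulated rejection at 1% is about 0.05% to 0.8%. For an illustrative effect of 1.2 recording SDs at one time point (an assumption; n = 22, m = 4), power at 1% is about 61-62% with a visit term. Without one it is about 52%, 44% and 29% at v = 0.25, 0.5 and 1. If the treatment-visit factor means period, the treatment-by-period interaction rejects about 1%.

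**One value per visit.** Rejection is about 1%, raw or as change. **Visit as error stratum:** the averaged treatment test rejects 0.8% to 1.3% in every simulated setting, which is 1% within simulation error.

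**The case against.** The strongest reply is that section 9 defines the primary outcome at one time point. With one value per visit, a subject random effect is the standard two-period crossover model and nothing is inflated. The sentence on recordings says when they are made, not that all of them enter the model. This stands as a possible reading, but the documents do not settle on it: the same section calls the recordings at all four times the primary measure.

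The second reply is the order of testing, and it also stands. A reader might infer that the trial's primary test as written rejects several times too often. The documents do not support that. Section 12 tests the interaction first, and that test is not inflated under either meaning of the treatment-visit factor. In simulation, the interaction at 1% followed by the 45-minute contrast at 5% rejects below 0.4% under the null for ρ from 0.1 to 0.5. The gate is not a remedy, however: under the time-point reading its conservatism comes from the same misplaced variance and costs power. Section 12 also does not say what is reported when the interaction is not significant. The averaged treatment effect is an obvious candidate, and it is the inflated quantity.

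Third, a reader might infer that day variation is missing from the error altogether, or that it biases the comparison. Neither is right. Part of it reaches the residual (the factor k), so it is under-weighted rather than absent. Allocation is 1:1 to the two sequences, so this is a question of precision, not of bias.

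**Conclusion.** The concern holds conditionally. If more than one recording per visit enters the model, the error structure in section 12 is wrong in both directions: too small for the averaged treatment effect and too large for treatment by time. The averaged test at nominal 1% then rejects about 2% to 15%, a range that rests wholly on the assumed ρ of 0.1 to 0.5. The figure of about 10% for changes from a shared baseline does not depend on ρ, but it assumes equal error variance at all recordings. The calculations also assume balanced, complete data.

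There is no inflation if one value per visit is analysed. No single error rate can be attached to the plan, because it does not fix which recordings are used. It is still more than a missing detail: on the multi-recording reading the written random-effects structure is incorrect, and one term corrects it.

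**What to change.** Before the blind is broken:

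1. Reconcile sections 9 and 12. State which recordings enter the primary model, whether as raw values or as changes; settle 40 against 45 minutes for the primary assessment; and say whether the treatment-visit factor is the period or the time point.
2. Then choose one of two routes. Either analyse the single primary time point, one value per visit, with the subject random effect as written. Or add a visit-within-subject random effect (or a within-visit covariance with Kenward-Roger degrees of freedom) to every model that uses more than one recording per visit. The extra term belongs only to the second route: with one value per visit it cannot be separated from the residual.
3. Say what is reported if the interaction is not significant.

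The cost is a few sentences and at most one model term, with no new data. Intervals for the averaged treatment effect become somewhat wider, and correct. The treatment-by-time test regains power.

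### The primary analysis states no unconditional sodium oxybate versus placebo test: the contrast waits on an interaction that, if visits means dosing visits, cannot see a consistent drug effect

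*Combined protocol and SAP*

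**What the plan says.** Section 12 analyses the primary outcome within each group by a linear mixed model "with treatment (sodium oxybate and placebo) and treatment visits as interacting fixed effects and a per subject random effect", at an overall level of 0.01. It continues: "If the interaction between the fixed effects is significant, the difference between treatments will be tested using linear contrasts of least-squares means", at an adjusted level of 0.05. It does not say what happens if the interaction is not significant, or whether the treatment term is read on its own.

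*Treatment visits* is not defined in section 12. Section 9a gives two candidates:

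- Dosing visits: "Eligible patients will require three visits, including one for the alcohol challenge test and two for sodium oxybate and placebo treatments".
- Assessments within a dosing visit, made "immediately before and 45, 180, 300 min after drug/placebo intake". Section 9a calls these time points, not visits.

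Allocation is a two-period, two-sequence crossover: "Patients will be allocated 1:1 to a treatment sequence #1 of sodium oxybate/placebo or sequence #2 of placebo/sodium oxybate". The primary outcome in section 9a "will be to determine the response of SD and VT symptoms to sodium oxybate 40 min after administration, compared to placebo".

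Section 12 also has an analysis with no condition attached: "As a secondary analysis, benefit ratio will be calculated as" the sodium oxybate effect minus the placebo effect, examined by a Friedman test at 0.01. It is labelled secondary.

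**The concern.** The single aim (section 2) is the clinical response to sodium oxybate, and the alternative hypothesis (section 11a) sets the drug against placebo. The primary analysis should therefore always deliver a drug-minus-placebo estimate and test. As written, that comparison comes second, after a test of a different question.

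Under the dosing-visit reading, the first question is whether the drug–placebo difference changes between visit one and visit two. A drug that works equally well at both visits gives no signal there, so a real and consistent benefit would usually go untested. Under either reading, leaving the treatment test unstated allows the deciding test to be picked after the data are seen.

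**Working it through.** **Inputs.** From the documents: 22 patients per group needed and up to 35 recruited (section 5a); two dosing visits, two sequences, 1:1 (section 9a); level 0.01 for the model and 0.05 for the contrast (section 12). Assumed, because the documents give no variance for the continuous ratings: a true effect δ = 0.80 SD of the paired drug–placebo difference, chosen so that the direct test has about 80% power at two-sided 0.01; and an intraclass correlation (ICC) of 0.3 to 0.8.

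**The plan's own figure.** The 22 in section 5a comes from a binomial test on 37/45 = 82.2%, not from this model. It reproduces one-sided at 0.0125 with an assumed null rate of 0.5: at least 17 successes in 22 has probability 0.0085 under the null and power 81.6%. Two-sided, power at 22 is 64.9%. The argument below does not depend on it.

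**Step 1: what the interaction measures under the dosing-visit reading.** Code drug +1, placebo −1; first visit +1, second visit −1.

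| Sequence | Visit | Treatment | Visit code | Product |
|---|---|---|---|---|
| 1 | first | +1 | +1 | +1 |
| 1 | second | −1 | −1 | +1 |
| 2 | first | −1 | +1 | −1 |
| 2 | second | +1 | −1 | −1 |

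The product is constant within a sequence, so the interaction is the sequence contrast. Each patient's sum over the two visits contains δ exactly once in either sequence, so δ drops out of the between-sequence difference. This is an identity. In four simulated data sets, the interaction statistic from a REML fit matched the between-sequence t statistic to four decimals in magnitude.

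**Step 2: how often the gate opens, no carryover.** The non-centrality is 0 for every δ, so the gate opens at its own level. In 40,000 simulated trials per setting (n = 22), it opened in 0.90–1.00% at 0.01 for effects of 0, 0.8, 1.5 and 3.0 SD. At δ = 0.80 and ICC 0.6 it opened in 0.99% at 0.01 and 4.92% at 0.05. Gate open and contrast significant: 0.94% and 4.68%. A mixed-model fit using a large-sample Wald test opened a little more often, in 1.8–2.5% of 400 runs per setting.

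**Step 3: the direct test.** Compare first-minus-second-visit differences between sequences. The expected contrast is 2δ = 1.6, with standard error √(1/11 + 1/11) = 0.426. Non-centrality is 1.6/0.426 = 3.75 on 20 df, critical value 2.845, power 80.5% (80.1% simulated). At n = 35 it is about 97%, while the gate still opens in about 1%.

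**Step 4: does the gate at least guard against carryover?** With carryover λ from drug into the following placebo visit, the direct contrast becomes 2δ − λ and the gate contrast becomes λ. At ICC 0.6 the SD of the patient sum is 2.0 (in SDs of the paired difference).

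| Carryover | Gate non-centrality (ICC 0.6) | Gate opens at 0.01 (simulated): ICC 0.6; range for ICC 0.8 to 0.3 | Direct-test power at 0.01 (simulated) |
|---|---|---|---|
| half, λ = 0.4 | 0.4/(2.0 × 0.426) = 0.47 | 1.8%; 1.3–2.7% | 49% |
| full, λ = 0.8 | 0.8/(2.0 × 0.426) = 0.94 | 4.4%; 2.3–9.1% | 20% |

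It does not.

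**Step 5: the time-point reading.** Treatment by four time points (pre-dose, 45, 180, 300 min), random patient intercept, 3-df interaction test at 0.01, n = 22, effect 0.80 SD of the paired difference at 45 min, 6,000 trials per scenario, visit-level variance 0 to 1 times residual.

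| Assumed time course | Gate opens |
|---|---|
| half the effect at 180 min, none at 300 | 50–63% |
| constant from 45 to 300 min | 56–70% |
| full at 180 min, none at 300 | 72–88% |

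The direct 45-minute test rejects in 80–82%. A repeat simulation agreed within about two percentage points.

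**The case against.** The strongest reply is that the gate is partly inferred. Section 12 does not contain the word *only*. Its model has a treatment term and an overall level of 0.01, so the conditional sentence could be ordinary follow-up wording, with the treatment term read directly. That may be the intention, but the text does not say so, and a primary test should not have to be inferred.

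Second, *treatment visits* may mean the time points. The primary measure is recorded four times per dosing visit, the dosing-visit model has no term for that, and adjusting the contrasts for multiplicity fits several post-dose times. Section 9a also says the effect lasts about 3.5–4 hours, which best matches the third time course in step 5, where the gate costs little power and can even open more often than the direct test rejects. This stands as a limit on the size of the problem. The contrast would still be conditional, however, and that model would have no period term. Section 9a's own vocabulary favours the dosing-visit reading.

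Third, the Friedman analysis carries no condition. But it is secondary, and it does not clearly test the drug–placebo difference against zero. One subtracted value per patient leaves nothing to rank within a patient; ranking the differences across time points would ask whether the difference changes over time.

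Fourth, the 0.80 SD effect and the carryover sizes are not from the documents, and a single short-acting dose makes large carryover look unlikely. Both points are fair. The roughly 1% gate rate without carryover depends on neither.

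**Conclusion.** The concern holds. Section 12 states no unconditional sodium oxybate versus placebo test for the primary outcome. If *treatment visits* means the two dosing visits and the condition is followed literally, the primary analysis declares a consistent drug effect in about 1% of trials (gate at 0.01) or 5% (gate at 0.05), against about 80% for a direct test at n = 22. The 1% and 5% are ceilings set by the gate for any effect size when there is no carryover; the 80% rests on the assumed 0.80 SD. If the term means time points, the loss ranges from serious to none, depending on time course and variance. Neither reading gives the trial a clearly stated primary test, so the text must be corrected before unblinding.

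**What to change.** Amend section 12 as follows.

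- Define *treatment visits* and remove the interaction condition.
- Make sodium oxybate minus placebo at one pre-specified post-dose time point the primary test within each group, at the plan's 0.01. Section 9a defines the outcome at 40 min but schedules the recording at 45 min, and the two must be reconciled.
- Fit treatment and period as fixed effects and patient as a random effect, and state how the pre-dose value enters.
- Report the estimate and confidence interval whatever any interaction shows.
- Report the sequence (carryover) contrast descriptively only, and state the interval between the dosing visits, which the readable text does not give.

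The test is fully specified only once the rated measure is named: section 10a says only that voice symptoms improve, while section 12 lists several ratings. The 0.01 here should also be squared with the 0.0125 used for sizing in section 5a.

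The cost is wording; no new data or patients are needed. The downside is that carryover is no longer a formal step. Real carryover would weaken the direct test (step 4), but the present gate gives almost no protection, opening in only about 2–4% of such trials at ICC 0.6.
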